### 9.3 Safety Population

*The safety population consists of all randomised subjects who receive at least one dose of IMP.*

*The safety population will be used for the analysis of safety and tolerability data. Subjects will be analysed as treated, regardless of the randomised treatment assigned, if this differs from that to which the subject was randomised.*

## 10 Analysis Variables

### 10.1 Population Flags

Population flags will be finalised and authorised by the Study Statistician and Sponsor during the blind review meeting prior to database lock as per definitions provided in section 9. These flags will be included in the analysis datasets.

### 10.2 Treatment groups

The following treatment variables along with corresponding numeric equivalents will be included as core variables in all analysis datasets:

- Planned / Actual Treatment Sequence : LAT8881 60 mg-Placebo, Placebo-LAT8881 60 mg
- Planned / Actual Treatment: LAT8881 60 mg, Placebo

### 10.3 Visits

Analysis visits will be defined as follows:

Visit as per CRF	Study Period	Analysis Visit
Visit 1 (Days -28 to -1)	-	Visit 1 (Screening)
Day 1, Visit 2	Period 1	Visit 2
Day 15, Telephone Visit 1	Period 1	-
Day 29, Visit 3	Period 1	Visit 3
Day 44, Telephone Visit 2	Period 2	-
Day 57, Visit 4	Period 2	Visit 4
Day 64, Visit 5 or Early Termination	Period 2	Visit 5 (End of Study)

Analysis timepoints for efficacy endpoints within each study period will be defined as follows:

Timepoint as per CRF	Analysis Timepoint
Before IMP was taken (Pre-dose)	Pre-dose
30 minutes after IMP taken (t=0.5 hrs)	30 minutes
1 hour after IMP taken (t=1 hr)	1 hour
1.5 hours after IMP taken (t=1.5 hrs)	1.5 hours
2 hours after IMP taken (t=2 hrs)	2 hours
4 hours after IMP taken (t=4 hrs)	4 hours
8 hours after IMP taken (t=8 hrs)	8 hours
24 hours after IMP taken (t=24 hrs)	24 hours

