9.3 First treatment period (Visit 2)

Subjects will return to the unit on Day 1 (Visit 2) with their diaries completed from Day -28 to Day -1 inclusive. If a subject has not experienced a migraine headache or menstrual bleeding (menstruating females only) during the 28-day period, the screening diary period may be extended to 35 days.

On Day 1, assessments including 12-lead ECG, vital signs, a targeted physical examination, recording of concomitant medications, review of the subject's diaries, blood and urine sampling for safety monitoring, and urine sampling for pregnancy testing in FOCBP, will be conducted. Results from safety monitoring tests are not required prior to randomisation.

Eligibility will be confirmed and subjects will be randomised to LAT8881 60 mg or placebo.

Subjects will leave the unit with their two diaries, and one dose of IMP and instructions to take the dose within one hour of the onset of a migraine headache of moderate to severe intensity (NRS ≥ 4). The headache diary will be used to record menstrual cycles and onset and nature of headaches (both migraine and non-migraine). The migraine diary will be used during a migraine headache to collect pain and symptom scores and concomitant medications before taking the IMP and at 0.5, 1.0, 1.5, 2, 4, 8 and 24 hours after taking the dose. No analgesics or antimigraine medication other than medications for routine prophylaxis not on the Prohibited medicines list may be taken within 24 hours prior to taking the dose of IMP. Rescue medication is permitted a minimum of 2 hours post dose. The subject's symptoms including nausea, photophobia and phonophobia plus the subject's most troublesome symptom if other than nausea, photophobia or phonophobia will be recorded immediately before dosing and at 0.5, 1.0, 1.5, 2, 4, 8 and 24 hours after taking the dose. Episodes of vomiting will also be recorded.

The subject will be instructed to phone the clinic within 24 hours (or one business day) of taking the dose.

On Day 15, if the subject has not phoned the clinic, the subject will be phoned to remind them to complete their diaries, and to phone the clinic when the dose has been taken.

Subjects will return to the clinic for Visit 3 within 5 business days after taking the dose or a maximum of 28 days after Visit 2. Subjects should be reminded to bring their diaries and medication container to the visit.

9.4 Visit 3

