9.7 Early withdrawal visit

An early withdrawal visit should be conducted within one week of the subject withdrawal, and/or a minimum 48 hours after last dose of IMP.

Subjects who are completing an early withdrawal visit will return with their diaries and unused IMP.

Blood and urine samples will be taken for safety analysis. 12-lead ECG, vital signs, concomitant medications, targeted physical examination results and adverse events will be recorded. Subjects will be asked to complete assessments for subject satisfaction.

10. Study endpoints

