#### 10.4 Study Periods

- Screening: Day -28 to Day -1
- Period 1: Visit 2 to Visit 3
- Period 2: Day after Visit 3 to Visit 5\*

\*Subjects who had a migraine event and took period 2 dose of IMP on the same day as Visit 3 will be identified and study periods for such subjects will be defined in the blinded review meeting.

Study periods for adverse events and concomitant medications will be assigned as below. •

Pre-IMP: Screening to first dose of IMP (irrespective of study period)

- Period 1: IMP date at period 1 to IMP date at period 2.
- Period 2: On and after IMP date at period 2.

Study periods will be considered to set analysis visits.

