#### 10.12.1 Safety Endpoints

For safety endpoints, measurement taken at Visit 2 will be considered as baseline for both study periods.

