## **11.9 Safety Analyses**

All safety summaries will be based on the Safety population and treatment groups as treated.

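### If SAP 10.3 is applied as written, the post-dose labs, vital signs and ECG of a subject who takes the Period 1 dose and withdraws before Visit 3 are tabulated in Period 2

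*SAP*

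**What the plan says.** SAP 10.3 maps each CRF visit to a study period and an analysis visit. Early termination appears only in the last row, "Day 64, Visit 5 or Early Termination". That row goes to Period 2 and to the Visit 5 (End of Study) analysis visit, and it is not split by time of withdrawal.

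SAP 10.4 defines the periods by visits. Period 1 runs from Visit 2 to Visit 3; the next line reads "Period 2: Day after Visit 3 to Visit 5". The section also says "Study periods will be considered to set analysis visits", but gives no rule for early termination. A separate rule based on dosing dates follows the sentence "Study periods for adverse events and concomitant medications will be assigned as below", so it is limited to those two data types. SAP 10.10 uses the same dose-date logic for adverse events.

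SAP 11.9.2.1, 11.9.3.1 and 11.9.3.3 summarise laboratory data, vital signs and ECG by treatment, both overall and separately within study period and visit. SAP 11.9 adds: "All safety summaries will be based on the Safety population and treatment groups as treated". For safety endpoints, SAP 10.12.1 states that "measurement taken at Visit 2 will be considered as baseline for both study periods".

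Protocol 9.7 collects blood, urine, ECG and vital signs at the early-withdrawal visit. On timing it says: "An early withdrawal visit should be conducted within one week of the subject withdrawal, and/or a minimum 48 hours after last dose of IMP".

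**The concern.** A subject who takes the first dose and withdraws within days has no Visit 3. The early-withdrawal visit is then the only scheduled source of post-dose labs, vital signs and ECG for that exposure. Under the SAP 10.3 row, the pre-dose Visit 2 record stays in Period 1 while the post-dose values and their changes from baseline move to Period 2, a period in which the subject took nothing.

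Safety and tolerability is a secondary objective. The Period 1 table for the treatment this subject took would show no post-dose value for someone who left soon after dosing. The protocol provides for withdrawal after certain adverse events (Protocol 7.11 and 12.1), so these may be subjects whose post-dose values are of particular interest. The same exposure would also be split across periods, with adverse events in Period 1 and labs, vital signs and ECG in Period 2.

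**Working it through.** The plan gives no figure for the number of such subjects. The check is a trace of the rules, followed by a bound on size.

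**1. Test subject (days assumed for illustration).** Visit 2 on Day 1, Period 1 dose on Day 8, early-withdrawal visit on Day 12, no Visit 3, no second dose.

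**2. Each rule applied to the Day 12 record.**

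- SAP 10.3 visit table: Period 2, end-of-study visit.
- SAP 10.4 visit-based periods: neither period. Period 1 needs Visit 3 to close it, and Period 2 needs Visit 3 to open it.
- SAP 10.4 and 10.10 dose-date rule: Period 1, because Day 12 falls after the first dose and there is no second dose. This rule covers adverse events (SAP 10.4 and 10.10) and concomitant medications (SAP 10.4) only.

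The three rules give three different answers. Only the 10.3 row names early termination, so it is the one a programmer would follow for labs, vital signs and ECG.

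**3. What the placement does.**

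- Within-period tables: the record leaves Period 1 and appears in Period 2.
- Summary by treatment overall: this pools the periods, so the record can stay under the drug taken. SAP 9.3, 11 and 11.9 all use actual treatment for safety, and this subject took only one. The SAP does not state this for the case.
- Change from baseline: still computable, because Visit 2 is the safety baseline for both periods.
- Listings: unchanged. Findings judged clinically significant also reach the adverse-event tables (Protocol 13.3) and are dated there by dose.

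**4. Who can be affected.** Protocol 9.3 says: "Subjects will return to the clinic for Visit 3 within 5 business days after taking the dose". With no public holidays assumed, a dose taken Monday to Friday makes Visit 3 due within 7 calendar days, a Saturday dose within 6 and a Sunday dose within 5. If Visit 3 is kept to schedule, the subject must withdraw inside those 5 to 7 days, miss Visit 3 and still attend the early-withdrawal visit. A subject who attended Visit 3 already has Period 1 post-dose results. One who attends no withdrawal visit has no record to misplace.

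**5. Weight of one subject.** Assume 20 to 26 subjects dosed in Period 1, split evenly between the two sequences. A Period 1 treatment cell then holds 20/2 = 10 to 26/2 = 13 subjects. One subject is 1/10 = 10.0% to 1/13 = 7.7% of that cell.

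**The case against.** **The end-of-study label follows the protocol.** Protocol 5.7 asks withdrawing subjects to attend an End of study visit, and SAP 10.6 treats the end-of-study and early-termination dates as alternatives. This stands. A reader might infer that the Visit 5 label is itself a mistake, since Visit 5 is a phone call and both schedules place early withdrawal in the Visit 4 column. The documents show only that they name this visit inconsistently. The label does not justify the Period 2 assignment.

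**The Visit 5 row already isolates these records.** Completers contribute no labs, vital signs or ECG at a phone contact, so any such values in that row come from early terminations. This largely stands. What remains wrong is the period under which the row is shown.

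**The treatment is not in doubt.** The as-treated rules point to the one drug taken. A reader might infer that the record will be counted under the treatment never received, or will drop out of safety reporting. The documents support neither reading.

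**The convention is deliberate.** SAP 11.1 also places early termination in Period 2 regardless of timing. That sentence governs the disposition table, where it does no harm. It gives no reason to separate a post-dose value from the dose that preceded it.

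**SAP 10.4 or the blinded review could settle it.** SAP 10.4 links study periods to analysis visits, but its visit-based definition places this subject in neither period. It refers dosing on the day of Visit 3 to the blinded review meeting; nothing refers early termination there.

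**Another Period 2 record can also lack a Period 2 dose.** A subject who attends Visit 4 without taking the second dose is one example. That is true, but such a subject has passed Visit 3 and so is in Period 2 under SAP 10.4 as well. The contradiction described here does not arise.

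**Conclusion.** The point holds as a minor one. As written, SAP 10.3 moves the only scheduled post-dose labs, vital signs and ECG of a subject dosed in Period 1 who leaves before Visit 3 out of the Period 1 by-treatment tables. That contradicts the period definition in SAP 10.4 and differs from the plan's treatment of the same subject's adverse events. The damage is limited to descriptive within-period safety tables.

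The number affected is not given, is probably very small and may be zero. A reader might take the 26 − 20 = 6 planned non-completers as the number at risk. That allowance also covers subjects who never treat a headache in one of the periods and those who leave after Visit 3, so it does not estimate this case. The weight of 1 in 10 to 1 in 13 per affected subject rests on the assumed even split of 20 to 26 dosed subjects.

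The eCRF and the Data Display Plan were not seen. Either could show that the tables are built differently, so the conclusion is conditional on SAP 10.3 being applied as written.

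**What to change.** In SAP 10.3, allocate early-termination labs, vital signs and ECG to the period and actual treatment of the last dose taken. This is the logic that SAP 10.10 already uses for adverse events. Show the record as an identifiable early-termination visit within that period.

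State that the same record contributes to the treatment-overall summary under the drug actually taken. Align SAP 10.4 with the revised row, so that a subject without Visit 3 has a defined period. Reconcile the names given to the withdrawal visit in Protocol 5.7, Protocol 9.7, SAP 10.6 and the two schedules. The SAP 11.1 disposition convention may stay.

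The cost is a short change of SAP wording, one derivation from dose and visit dates already held, and one sparse row in the laboratory, vital-sign and ECG tables. No new data are needed.

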#### 10.4 Study Periods

- Screening: Day -28 to Day -1
- Period 1: Visit 2 to Visit 3
- Period 2: Day after Visit 3 to Visit 5\*

\*Subjects who had a migraine event and took period 2 dose of IMP on the same day as Visit 3 will be identified and study periods for such subjects will be defined in the blinded review meeting.

Study periods for adverse events and concomitant medications will be assigned as below. •

Pre-IMP: Screening to first dose of IMP (irrespective of study period)

- Period 1: IMP date at period 1 to IMP date at period 2.
- Period 2: On and after IMP date at period 2.

Study periods will be considered to set analysis visits.

#### 10.5 Completion Flags

- Subjects are considered to have completed period 1 when Visit 3 is completed.
- Subjects are considered to have completed period 2 when Visit 4 is completed.
- Subjects are considered to have completed study when EOS at Visit 5 is completed.

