5.4 Number of planned subjects

It is planned to have 20 subjects complete the study, defined as taking one dose of IMP in each treatment period and attending the followup (End of study) visit.

Assuming up to 20% of subjects do not treat one migraine headache in each treatment period or dropout of the study, 26 subjects will be enrolled in the study.

If the dropout rate or non-completion rate is higher than anticipated, additional subjects may be enrolled to ensure 20 subjects complete the study.

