## **4.2 Sample Size Justification**

*It is planned to have 20 subjects complete the study, defined as taking one dose of IMP in each treatment period and attending the follow-up (End of study) visit.*

*Assuming up to 20% of subjects do not treat one migraine headache in each treatment period or dropout of the study, 26 subjects will be enrolled in the study.*

[figure not shown]
*If the dropout rate or non-completion rate is higher than anticipated, additional subjects may be enrolled to ensure 20 subjects complete the study.*

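### The SAP's completed-study flag rests on Visit 5 alone, so the reported completer count could exceed the number who meet the dose-based definition behind the target of 20

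*SAP*

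**What the plan says.** Protocol 5.4 sets the trial's only size commitment: "It is planned to have 20 subjects complete the study". It makes a completer of a subject only when two conditions are met together, and words them as "defined as taking one dose of IMP in each treatment period and attending the followup (End of study) visit". SAP 4.2 repeats the definition almost word for word: "defined as taking one dose of IMP in each treatment period and attending the follow-up (End of study) visit". Both documents link this number to possible further recruitment; in the SAP, "additional subjects may be enrolled to ensure 20 subjects complete the study".

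SAP 10.5 then defines three completion flags by visit only. For period 1, "Subjects are considered to have completed period 1 when Visit 3 is completed". Period 2 is treated the same way with Visit 4, and for the study as a whole "Subjects are considered to have completed study when EOS at Visit 5 is completed". None of the three mentions a dose.

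SAP 11.1 puts the number who completed the study in the disposition table (Table 14.1.1), again with no dosing condition. SAP 8.1, which lists changes from the protocol's planned analyses, does not mention a changed definition of completion.

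**The concern.** One word has two meanings, and the difference will arise in ordinary conduct. The protocol synopsis has a subject who has not taken IMP return for Visit 3 no later than 28 days after Visit 2, and for Visit 4 no later than 28 days after Visit 3. Visit 5 is a telephone call a week after Visit 4, whether or not a dose was taken. A subject with one dose or none can therefore be flagged as completing both periods and the study.

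Two things are at stake. First, a reader will compare the completed-study row with the target of 20, although the row is not built to the target's definition. Second, SAP 8.1 lets the choice of a mixed model for the symptom and satisfaction endpoints depend on how many subjects complete the two periods, and SAP 10.5 holds the SAP's only definition of completing a period. If undosed attenders were counted, completion could look high enough at the blind review to do without the mixed model. Subjects with data from one period would then drop out of those treatment comparisons, which is the loss SAP 8.1 set out to avoid.

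**Working it through.** **Inputs.** From Protocol 5.4: target 20; enrolment 26 ("26 subjects will be enrolled in the study"); loss allowance 20% ("Assuming up to 20% of subjects do not treat one migraine headache in each treatment period or dropout of the study"). The allowance pools untreated attacks and dropout and gives no split. Protocol 14.2 states that there is no formal sample size calculation, so there is no power figure to reproduce.

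**The plan's own figure.** 20 / (1 − 0.20) = 25. The plan enrols 26, one more. Expected protocol-defined completers at the full allowance: 26 × 0.80 = 20.8. Expected loss: 26 × 0.20 = 5.2.

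**What the SAP flag would count.** Let s be the share of the lost subjects who still reach Visit 5 without having been dosed in both periods. The documents do not give s, so the whole range from 0 to 1 is an assumption.

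- Expected flagged = 20.8 + 5.2s.
- Overstatement = 5.2s / 20.8 = 25% × s.
- Chance that a subject is flagged = 0.80 + 0.20s.
- With 26 independent subjects and a true loss of 20%, the chance of at least 20 protocol-defined completers is 0.747. Every such completer is also flagged, so the chance that the row shows 20 or more while true completers number fewer than 20 is P(flagged ≥ 20) − 0.747.

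| s | Expected flagged | Overstatement | P(flagged ≥ 20) | P(flagged ≥ 20, true completers < 20) |
|---|---|---|---|---|
| 0 | 20.8 | 0% | 0.747 | 0 |
| 0.25 | 22.1 | 6.25% | 0.917 | 0.169 |
| 0.50 | 23.4 | 12.5% | 0.988 | 0.241 |
| 0.75 | 24.7 | 18.75% | 1.000 | 0.252 |
| 1 | 26.0 | 25% | 1.000 | 0.253 |

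The last column uses unrounded probabilities.

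**If the loss is smaller.** The allowance is an upper figure. For a loss rate L the largest overstatement is L / (1 − L): 25% at L = 0.20, but 0.10 / 0.90 = 11% at L = 0.10.

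**Early termination.** SAP 10.3 maps both Visit 5 and early termination to the analysis visit for end of study, and Protocol 5.7 asks withdrawing subjects to attend an end-of-study visit. The flag does not say that such a visit is not completion. This cannot raise the ceiling of 26, but it is a second route by which a subject without both doses could be counted.

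**What depends on the flag.** The full analysis set is defined by randomisation (SAP 9.1). The per-protocol and safety populations both require at least one dose (SAP 9.2, 9.3). Paired differences use only subjects who took IMP both times (SAP 10.15.1). The primary mixed model runs on the per-protocol population (SAP 11.8.1.3). None of these refers to SAP 10.5.

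**The case against.** The strongest reply is that this is a label. The exposure tables in SAP 11.7 show how many subjects were exposed in one period or in both, each paired summary carries its own n, and SAP 8.1 openly expects subjects with one period only. SAP 11.1 also already reports attendance at each visit. All of this stands, and it limits the point to a reported count and one analysis trigger. It does not remove the contradiction: no described table gives subjects with both doses and Visit 5, which is the quantity the target of 20 refers to.

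It also stands that the protocol defines completing the study but not completing a period. Protocol 5.1 moves subjects on after one treated attack or after 28 days, so the two visit-based period flags do not conflict with it. The conflict is with the study flag. On the SAP 8.1 trigger, the surrounding text is about subjects who took IMP in one or both periods, so a sensible team would probably read it as dosed. The wording still leaves the other reading open.

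A reader might infer three stronger things that the documents do not support:

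- *Recruitment could stop short of 20 treated pairs.* If recruitment stopped at 20 flagged subjects and s were 1, only 20 × 0.80 = 16 would be pairs, and the 95% confidence half-width for a paired mean would go from 0.468 to 0.533 SD (+14%). But the extra-enrolment rule sits beside the dose-based definition in both documents, is permissive, and is not linked to SAP 10.5.
- *The overstatement is 25%.* That needs every lost subject to attend Visit 5 and no dropout at all.
- *Efficacy results are biased.* No primary or paired estimate uses the flag.

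**Conclusion.** The point holds as an inconsistency with a limited consequence. SAP 10.5 contradicts Protocol 5.4 and SAP 4.2 on what completing the study means, and the disposition row could exceed the number of protocol-defined completers by 0% to 25%. That range assumes 26 enrolled, the full 20% loss and an unknown split between untreated attacks and dropout. On the same assumptions, the chance that the row meets 20 while true completers do not is between 0 and about 0.25. The trigger in SAP 8.1 is ambiguous for the symptom and satisfaction endpoints only. It should be corrected before database lock because the trial's one size commitment ought to be reported on its own definition, but the credibility of the primary result does not depend on it.

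**What to change.** In SAP 10.5, define study completion as IMP taken in both periods and Visit 5 completed, and state that an early termination visit does not count. Report that number in Table 14.1.1 against the target of 20.

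The period flags may stay visit-based if they are labelled as visit completion. Subjects who attend through Visit 5 without being dosed in both periods need their own disposition category; otherwise they would be neither completed nor terminated in SAP 11.1.

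In SAP 8.1, state that the mixed-model decision depends on the number of subjects dosed, with efficacy data, in both periods.

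The cost is one redefined flag, one added category and one clarified sentence, with no new data and no change to conduct. The downside is a possibly lower reported completer count and a slightly longer disposition table.
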